14.7 Efficacy Analysis

14.7.1 Primary Efficacy Analysis

The repeat opioid OD or opioid-related death primary endpoint analysis will be performed using Cox proportional regression and compare the SUBLOCADE treatment arm to historical and concurrent control data. Propensity scores will be used to match study participants to controls. Repeat OD and deaths (measured as time-to-event or censored at 6 months post index OD) will be tracked using subject reports, electronic medical records and state death registries. Events will be counted within the 6 months of treatment period for all treated subjects.

Propensity score analysis will be used in the analysis of SUBLOCADE vs. the control for time to repeat OD or opioid-related death. Study subjects will receive a propensity score that will be matched to propensity scores in the control data. The propensity score, p , will also be used as a weight in the Cox proportional hazards model. All SUBLOCADE treatment group subjects will have a weight of $p=1$ and patients in the control groups will be weighted by $p/(1-p)$. Here p can be viewed as the probability that the control subject would have been a study participant if the study were performed during their treatment.

The propensity score will be estimated by fitting a logistic regression on a dataset consisting of the consenting subjects (subjects in the SUBLOCADE arm at VCU) and the controls. The response variable will be consent to treatment; predictors will include baseline characteristics such as subject age, gender, county, race and insurance status. This model will be used to generate the predicted probability of consent to participate among the controls.

The Cox proportional hazards model will use the controls as the reference group and code the SUBLOCADE arm as a factor variable. The analysis will test the coefficient for the SUBLOCADE arm versus the controls from the Cox regression, with the interpretation of the exponential (coefficient) as the hazard ratio for time to repeat OD or opioid-related death in subjects consenting to the active treatment group versus the control cohorts.

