The probabilities for the control cohort will be used as weights in the Cox proportional hazards model. The weights serve to make the control cohort appear similar to the treatment group on the observed baseline characteristics; this will be checked using covariate balance diagnostics. The weights will provide greater weight for control patients who likely would have participated if offered a prospective trial of SUBLOCADE and lesser weight for patients unlikely to have consented.

In addition, the results will be illustrated with a Kaplan-Meier curve.

The analysis will take place once all subjects have completed the trial and sufficient time has passed to allow the state death registries to be updated.

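### Section 14.7.1 matches controls on the propensity score and then weights them by p/(1−p) from the same model; if matching discards many controls, the second step over-corrects and can bias the primary hazard ratio

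*Combined protocol and SAP*

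**What the plan says.** Section 14.7.1 sets out the adjustment for the non-randomised primary comparison, which is to "compare the SUBLOCADE treatment arm to historical and concurrent control data".

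- Matching appears twice: "Propensity scores will be used to match study participants to controls", and again "Study subjects will receive a propensity score that will be matched to propensity scores in the control data".
- Weighting is then added: p "will also be used as a weight in the Cox proportional hazards model". Treated subjects get weight 1, and "patients in the control groups will be weighted by" p/(1−p).
- There is one model for p: "The propensity score will be estimated by fitting a logistic regression on a dataset consisting of the consenting subjects" and the controls. Nothing says that it is re-estimated in a matched set.
- The purpose is stated for the weights only: "The weights serve to make the control cohort appear similar to the treatment group on the observed baseline characteristics". Balance diagnostics are promised, without an action if balance fails.
- Later in the same section the weights are described differently: "The probabilities for the control cohort will be used as weights in the Cox proportional hazards model". That is p, not p/(1−p).

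The matching algorithm, ratio, caliper and replacement rule are not given. Section 6.1 gives 2015 as the start year for controls but no number. The 198 controls in Section 14.2 are historical controls only. The primary efficacy row of Table 2 refers to propensity scores within the Cox regression and does not mention matching.

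**The concern.** Matching and odds weighting are alternative ways to reach the same target, a control group with the covariate distribution of the treated subjects. The weight p/(1−p) is correct for the population in which p was estimated, here treated subjects plus all controls. Once matching has pruned that pool towards the treated group, the kept controls no longer have the pool's distribution. The same weights then tilt them a second time, and the imbalance returns with its sign reversed.

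This is the main protection against confounding that Section 14.7.1 describes. If traits that predict consent also predict higher overdose risk, the over-corrected controls are too high-risk and an inactive drug looks protective. If those traits predict lower risk, it looks harmful.

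**Working it through.** **Inputs from the documents.** Section 14.2: 99 treated, 198 historical controls, 6-month event rates of 3% and 11.5%, 80% power at 5% type I error. Section 14.7.1: the weights, the single model for p, and censoring at 6 months.

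**The plan's own figure.** The 80% power for 99 versus 198 reproduces with a one-sided 5% Fisher exact test (80.25%; two-sided 73.0%). The implied planned hazard ratio is ln(0.97)/ln(0.885) = 0.25.

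**Closed form.** Assume one covariate x, distributed N(0,1) in controls and N(d,1) in treated subjects. Then p/(1−p) is proportional to exp(d·x).

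- Full pool: N(0,1) times exp(d·x) gives N(d,1), so the treated-minus-control difference is 0.
- Controls already matched to N(d,1), times exp(d·x), give N(2d,1). The difference is d − 2d = −d.
- With a hazard ratio of 2 per SD and d = 0.5, the rare-event hazard ratio under no effect tends to exp(−0.5 × ln 2) = 0.71.

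**Simulation.** Assumed: inactive drug, 99 treated, control risk 11.5%, one normal covariate, p fitted on treated plus the full pool. Matching is 2:1 greedy nearest-neighbour on logit p without replacement, followed by a Cox model with the p/(1−p) weights and robust standard errors. There were 5,000 datasets per main cell. The share of controls discarded is 1 − 198/pool. A false protective result is robust z below −1.96, nominal 2.5%.

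| Control pool | 198 | 220 | 250 | 300 | 500 | 1,500 |
|---|---|---|---|---|---|---|
| Discarded | 0% | 10% | 21% | 34% | 60% | 87% |
| *Weak: 0.25 SD shift, HR 1.3 per SD* | | | | | | |
| Standardised difference | 0.00 | −0.09 | −0.15 | −0.20 | −0.23 | −0.24 |
| Median HR | 1.00 | 0.98 | 0.96 | 0.96 | 0.93 | 0.93 |
| False protective | 1.9% | 1.8% | 2.0% | 3.0% | 3.0% | 2.8% |
| *Strong: 0.5 SD shift, HR 2 per SD* | | | | | | |
| Standardised difference | 0.00 | −0.08 | −0.17 | −0.27 | −0.41 | −0.48 |
| Median HR | 1.00 | 0.97 | 0.92 | 0.86 | 0.78 | 0.73 |
| False protective | 2.0% | 2.3% | 2.7% | 5.0% | 10.1% | 13.8% |
| *Lowers risk: 0.5 SD shift, HR 0.5 per SD* | | | | | | |
| Median HR | 0.99 | 1.09 | 1.16 | 1.25 | 1.35 | 1.38 |

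Odds weights alone on all controls gave a difference of 0.00 and a hazard ratio of 0.98 to 1.00 throughout. Their false protective rate was 1.5–2.2% in the weak case and 1.6–2.1% in the strong case.

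**When there is no bias** (0.5 SD shift and HR 2 per SD unless stated, pools 300–1,500):

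- Trimming only to the treated score range drops 3% of controls: HR 1.01.
- Re-fitting p after matching: HR 1.00–1.04.
- Covariate not prognostic: HR 1.00.
- No group difference: HR 0.99–1.00.

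**A pool of exactly 198 is not always safe.** A 0.2-SD caliper in the strong case gives HR 0.94 (difference −0.14 SD) if unmatched treated subjects stay in, and 0.87 (−0.24 SD) if they are dropped.

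**Larger samples** (990 treated, 0.5 SD shift, log-HR 0.7 per SD, inactive drug; 33%, 60% and 80% discarded):

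- Both steps: HR 0.85, 0.76, 0.71.
- Weighting alone: 0.99, 1.00, 0.98.
- Matching alone: 1.12, 1.02, 0.98.

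Under the planned effect (true HR 0.249, 99 treated, 990 controls), the median HR is 0.19 with both steps, 0.25 with weighting alone and 0.26 with matching alone.

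**The case against.** The strongest reply is that *match* is loose wording and weighting alone was meant. The formula, the stated purpose and the balance check all concern weights. Section 14.7.1 also says that controls unlikely to have consented get less weight, which presumes that they are still in the model. No matched set, ratio or caliper is defined anywhere. This may well be the intention, but matching is stated twice and weighting is introduced as an addition, so an analyst following the text would do both. The argument supports weighting as the repair; it does not remove the contradiction.

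Second, the harm needs several conditions that the documents do not establish: matching that discards, a pool well above 198, no re-fit, and covariates such as age, county or insurance that are strongly related to both consent and overdose. This stands. Under weak confounding there is little inflation, and a shift of log(0.93) = −0.07 is about one-fifth of the standard deviation of the log hazard ratio (about 0.36). On pool size, however, 198 counts historical controls only. If all 198 are used and concurrent controls are pooled with them, the pool is larger.

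Third, the balance check may well show a reversed imbalance of −0.27 to −0.48 SD. That is true, but no response to a failed check is stated. The analysis comes after all subjects have completed the trial, so removing the matching step then would be a late change to the primary method.

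**Conclusion.** The concern holds. Read literally, Section 14.7.1 adjusts twice with one score. If nearest-neighbour matching discards a material share of controls, and the score covariates differ between groups and predict overdose, the primary hazard ratio is biased. The direction depends on whether those covariates raise or lower risk.

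Under the stated assumptions the no-effect hazard ratio moves to 0.93 at worst in the weak case, and to 0.73 or 1.38 in the strong cases. The false protective rate reaches 13.8% in the strong case where the covariate raises risk. There is no double adjustment if all controls are kept, if only controls outside the treated score range are trimmed, or if p is re-fitted after matching. The bias alone would not produce the planned hazard ratio of about 0.25. The mechanism is certain; its size in this trial cannot be known from the documents. Because the primary estimator is not uniquely defined, this should be settled before outcomes are analysed.

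**What to change.** In Section 14.7.1:

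1. Delete the two matching sentences and the word *also*.
2. State that all eligible controls are kept, with treated subjects weighted 1 and controls weighted p/(1−p), and that the Cox model uses a robust (sandwich) variance.
3. Where the weights are later called probabilities, call them the odds p/(1−p).

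Weighting alone is preferred because the section already gives its formula and purpose, and it left no imbalance at any pool size tested. That test used one normal covariate and a correctly specified model, so the planned balance diagnostics are still needed. Matching without weights can be a sensitivity analysis, with its ratio, caliper and replacement rule stated.

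The cost is wording and slightly more analysis work; no new data are needed. Odds weights reduce the effective number of controls. With one normal covariate the share kept is exp(−d²): exp(−0.0625) = 0.94 for a 0.25 SD shift and exp(−0.25) = 0.78 for a 0.5 SD shift.

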- Predictability of treatment response based on impulse control as measured by decision making in the delay discounting task, and opioid cravings/valuation as measured by the brief opioid demand task.
- Healthcare resource utilisation as compared to the historical control (2015-2018) obtained from VCU anonymized health records.
- Treatment effectiveness as measured by Treatment Effectiveness Assessment (TEA), medication satisfaction as measured by the Medication Satisfaction Questionnaire (MSQ), and employment, presentism and absenteeism as assessed by the Work Productivity and Activity Impairment Questionnaire: Specific Health Problem (WPAI:SHP).

Safety Assessments:

Safety assessments include the proportion of subjects with AEs of the following types at any time during the treatment period: at least 1 AE, a drug-related AE, an SAE, a serious and drug-related AE, or an AE leading to treatment discontinuation.

Additional safety assessments include laboratory assessments, brief physical examinations, vital signs and concomitant medications. Worsening or initiation of withdrawal symptoms, based on observation and subject self-report, will be evaluated during Visit 1 (ED, inpatient unit or Clinic) after SUBOXONE and SUBLOCADE. If participants experience precipitated withdrawal, they will be treated symptomatically with medication as described in section 8.4 below.

Health Economics and Outcomes Assessments:

Health economics and outcomes assessments include the include Healthcare Resource Utilization questionnaire (HCRU), the Treatment Effectiveness Assessment (TEA), the Medication Satisfaction Questionnaire (MSQ), and Work Productivity and Activity Impairment Questionnaire: Specific Health Problem (WPAI-SHP).

Statistical Methods:**Prospective Analyses for the Primary and Key Secondary Endpoints:**

The primary endpoint, numbers of subjects who have a repeat OD or OD related death will be analysed using a Cox proportional hazards model controlling for route of administration and comorbid substance use disorder compared to a historical control group and to concurrent subjects who decline SUBLOCADE treatment.

[figure not shown]
The secondary endpoint, treatment engagement as measured by attending the outpatient clinic and receiving subsequent buprenorphine treatment at 3 and 6 months will be analysed using a Cox proportional hazards model comparing patients with primarily intravenous vs non-intravenous routes of opioid use.

Planned Analyses:

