13.1.1 Historical and Concurrent Control Data

The historical and concurrent control data used for exploratory OD comparison analyses will be provided by Virginia Commonwealth University as an anonymized data extract from their electronic medical record system beginning in 2015. Data will include, but not be limited to; demographics, discharge diagnoses and status and ICD 9/10 codes.

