14.6 Demographic and Baseline Characteristics Analyses

Demographic and baseline characteristics, including gender, race, age, weight, height and disease history will be summarized by treatment group using descriptive statistics. Disease history will include but is not limited to drug use history, history of MAT and previous Ods. Qualitative variables, e.g. gender and race will be summarized using frequencies; quantitative variables, e.g. age, weight, height will be summarized using e.g. mean, SD, median, minimum and maximum.

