14.7.4 Subgroup Analysis

Primary analyses will be repeated but adding an explanatory class variable of subjects identified as injectors vs. non-injectors at Week 1 Day 1 (Visit 1).

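### The primary Cox model is stated two ways, and its open propensity covariate list names no clinical severity variable, so balance on severity is not assured

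*Combined protocol and SAP*

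**What the plan says.** Two current parts of the document describe the primary analysis.

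- **Synopsis, Statistical Methods:** a Cox model "controlling for route of administration and comorbid substance use disorder", comparing treated subjects with the historical group and with concurrent patients who decline.
- **Section 14.7.1:** a Cox model that "will use the controls as the reference group and code the SUBLOCADE arm as a factor variable". Treated subjects get weight 1 and controls get p/(1−p). For the logistic model that produces p, "predictors will include baseline characteristics such as subject age, gender, county, race and insurance status".

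Other sections bear on the point:

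- Table 2 (14.7.2) gives the primary method as propensity scores within Cox regression and lists no covariates.
- Section 14.7.4 repeats the primary analysis with injector status at Visit 1 added, as a subgroup analysis.
- Section 14.6 lists "drug use history, history of MAT and previous Ods" as disease history to be summarised descriptively.
- Section 14.7.1 also plans balance diagnostics on the observed baseline characteristics, which are not fully listed.
- Section 13.1.1 says the control extract, starting in 2015, holds "demographics, discharge diagnoses and status and ICD 9/10 codes", without being limited to these.
- Section 5.3 excludes severe benzodiazepine or alcohol use disorder from the treated group. Section 6.1 draws controls from VCU emergency department overdose visits from 2015 and states no matching exclusion.

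**The concern.** The study is open-label and not randomised, so the validity of the primary hazard ratio depends on the adjustment. An analyst following the Synopsis and an analyst following 14.7.1 would fit different models. The version with operational detail names no measure of how ill the patients were.

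The Synopsis itself treats comorbid substance use as worth adjusting for, and the eligibility rules select the treated group on exactly that factor. Weights built on sociodemographic variables are not designed to remove such a difference. Because the list is also open, covariates could be settled after outcomes are known.

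**Working it through.** **1. Where each clinical factor appears.**

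| Factor | Synopsis model | Cox terms in 14.7.1 | Named propensity predictors in 14.7.1 | Elsewhere in section 14 |
|---|---|---|---|---|
| Route of use | yes | no | no | 14.7.4, subgroup repeat |
| Comorbid substance use disorder | yes | no | no | not in the primary analysis |
| Prior overdoses | no | no | no | 14.6, descriptive |
| Prior MAT | no | no | no | 14.6, descriptive |

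**2. The plan's own figure.** Section 14.2 states 80% power for 99 treated subjects and 198 historical controls, 3% against 11.5%, at a 5% type I error rate. Exact power of Fisher's test, enumerated over both binomials, is 80.25% one-sided and 73.0% two-sided. The stated figure therefore reproduces as a one-sided test. The plan does not state sidedness, so both are shown below. The calculation makes no allowance for confounding. Expected events at the design rates are 99 × 0.03 + 198 × 0.115 = 2.97 + 22.77 ≈ 26.

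**3. Illustration of an unbalanced severity factor.** The prevalences and hazard ratios here are assumptions; none is in the documents. Suppose the drug has no effect, the factor has hazard ratio HR, and its prevalence is pT in treated subjects and pC = 50% in controls. The apparent ratio is approximately

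b = [1 + pT(HR − 1)] / [1 + pC(HR − 1)].

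For HR 2 and pT 30%: 1.3 / 1.5 = 0.87. For HR 3 and pT 30%: 1.6 / 2.0 = 0.80. For HR 2 and pT 70%: 1.7 / 1.5 = 1.13.

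To get the chance of a falsely significant benefit, set the treated risk to r = 0.115 × b and use the normal approximation to a two-proportion test:

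Φ[(0.115 − r − z·SE0) / SE1],

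where SE0 is the pooled and SE1 the unpooled standard error at 99 and 198, and z is 1.645 (one-sided 5%) or 1.96 (benefit tail of a two-sided 5% test). For HR 2 and pT 30%: r = 0.0997, SE0 = 0.0385, SE1 = 0.0377, so Φ[(0.0153 − 0.0633) / 0.0377] = Φ(−1.27) = 10.1%.

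| HR | pT vs pC | Apparent ratio | False benefit, one-sided (nominal 5%) | Benefit tail, two-sided (nominal 2.5%) |
|---|---|---|---|---|
| 1.5 | 40% vs 50% | 0.96 | 6.2% | 3.2% |
| 2 | 30% vs 50% | 0.87 | 10.1% | 5.5% |
| 3 | 30% vs 50% | 0.80 | 14.1% | 8.0% |
| 3 | 20% vs 50% | 0.70 | 22.2% | 13.6% |
| 2 | 70% vs 50% | 1.13 | 2.3% | 1.1% |
| 3 | 70% vs 50% | 1.20 | 1.5% | 0.7% |

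This is an unweighted binary approximation to the weighted Cox analysis. It shows scale only.

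**4. What can be measured alike in both groups.**

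- *Comorbid disorders:* the control extract carries diagnoses and ICD codes, so these can be coded. For treated subjects the screening checklist covers only opioid, alcohol and sedative disorders. Others, such as stimulants, wait for the M.I.N.I. at Visit 2, after the first dose (8.1.1).
- *Prior overdoses:* VCU has already counted repeat overdoses per patient (Synopsis rationale; 14.2), so encounters can be linked. A control with a 2015 index visit, however, has almost no look-back in an extract that starts in 2015.
- *Route and prior MAT:* section 13.1.1 names neither for controls. Section 14.7.2 takes route from the M.I.N.I., while 14.7.4 uses injector status at Visit 1.

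**5. Variance.** Section 14.7.1 names no variance estimator for the weighted Cox model.

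**The case against.** The strongest reply is that the plan leaves the list illustrative. Section 14.6 counts drug use history, MAT history and previous overdoses as baseline characteristics, and balance diagnostics are planned. A reader might infer that the model balances demographics only and ignores prior overdoses. The documents do not support that: clinical predictors are unspecified, not ruled out. Nor has route vanished, since 14.7.4 adds injector status. What remains is that a subgroup repeat is not the primary model, and comorbid substance use disorder appears nowhere in section 14's primary analysis.

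A reader might also infer that severity is left unbalanced in a way that flatters the drug. That does not follow either. Section 5.3 removes some severe comorbidity from the treated group, but 5.2 requires moderate to severe opioid use disorder and 6.1 states no such requirement for controls, which could make treated subjects the more severe. The illustrated ratios are also modest beside the design contrast of 3 / 11.5 = 0.26.

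Measurement is a fair objection too. Treated subjects' history comes partly from interview, and those referred by EMS after refusing transport may have no emergency department record of the index event. Adding covariates recorded differently in the two groups could introduce bias of its own. This shapes the remedy but does not remove the inconsistency.

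**Conclusion.** The point holds as an inconsistency together with incomplete pre-specification. The Synopsis and 14.7.1 give different primary models, and the propensity list names no clinical severity variable although eligibility screens the treated group on one. Balance on severity is therefore not assured.

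The documents fix neither the sign nor the size of any resulting bias. On the assumed figures, the apparent hazard ratio under no effect runs from 0.70 to 0.96 if treated subjects are less severe. It exceeds 1, up to 1.20 in the cases shown, if they are more severe. With about 26 expected events, either direction could matter to the primary test, and the change should be made before the analysis.

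**What to change.** - **Reconcile** the Synopsis and 14.7.1 so that one primary model is stated.
- **Close the covariate list** in 14.7.1. To the existing predictors add comorbid alcohol, sedative and stimulant use disorder and prior opioid overdose encounters.
- **Measure alike:** derive these from the same electronic record source, with the same fixed look-back before the index overdose, in both groups.
- **Check balance** on every variable in the closed list, the added ones included.
- **Route and prior MAT:** include each only if it can be obtained comparably for controls. If route cannot, say so, remove it from the Synopsis model and keep it as the 14.7.4 analysis.
- **Variance:** specify a robust (sandwich) or bootstrap variance for the weighted Cox model.

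The cost is SAP wording, some ICD coding, slightly more variable weights, and possible loss of controls whose index visit is too early for the common look-back.

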14.2 Sample Size

The study will be powered based upon the primary endpoint, repeat opioid OD and death compared to historical and concurrent control data.

Rationale for sample size: Power calculations: sample size was calculated based on a primary outcome measure of reduced repeat opioid OD rates. Previous research has shown self-reported repeat lifetime OD rates of 15-23% for patients who were seen for an opioid OD (Morizio, Baum et al. 2017).

Based on VCU health system data, for patients seen in the ED for an opioid OD in 2016, 11.5% of those patients were either seen again in the ED for an opioid OD or had died based on Virginia Department of Health death registry data within 6 months after their initial ED visit. Based on power calculations below, with a 3% repeat OD or death rate for the novel treatment group vs. the 11.5% treatment as usual rate in the historical control group, with 99 participants in the novel treatment group and 198 participants in the historical control group there will be a power of 80% at a type I error rate of 5%. See table below. If there is a less than 3% repeat OD rate in the intervention group there will be greater than 80% power.

Fixed Power of 0.80 and sample size for equivalent or non-equivalent numbers of participants per group (intervention vs. historical treatment as usual)

repeated OD/death rate	Stat method	n1:n2 (1:1, 2:1 or :1 ratio)		
11.5% vs 2%	Z-test	86:86	117:59	148:49
	Nonparametric	94:94	148:74	198:66
11.5% vs 3%	Z-test	115:115	160:80	204:68
	Nonparametric	131:131	198:99	265:88

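### The primary Cox test is not named and has no rule for zero treated events; if it is a Wald test, power does not rise as the treated rate falls below 3%

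*Combined protocol and SAP*

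**What the plan says.** Section 14.7.1 fits a Cox model with controls as the reference group. On weighting it says "The propensity score, p , will also be used as a weight in the Cox proportional hazards model": treated subjects have weight 1 and controls p/(1-p). On inference it says "The analysis will test the coefficient for the SUBLOCADE arm versus the controls from the Cox regression". The effect measure is that coefficient exponentiated and read as a hazard ratio. The section does not say whether the test is Wald, likelihood-ratio or score, whether it is one- or two-sided, or which variance goes with the weights. A Kaplan-Meier curve is planned as illustration. Table 2 adds only that propensity scores are used within Cox regression.

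Section 14.2 sizes the trial on two proportions. For controls, "11.5% of those patients were either seen again in the ED for an opioid OD or had died" within 6 months. The scenario is "with a 3% repeat OD or death rate for the novel treatment group", and the group sizes are given as "with 99 participants in the novel treatment group and 198 participants in the historical control group". On lower treated rates the section adds: "If there is a less than 3% repeat OD rate in the intervention group there will be greater than 80% power". The sizing table has rows for a Z-test and a nonparametric test, at treated rates of 2% and 3%. It has no Cox row.

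**The concern.** The plan expects about three treated events and hopes for fewer. A test that depends on a finite coefficient and its standard error has nothing to work with when the treated group has no events. That is the best result the trial could produce, and it becomes more likely as the drug works better. The plan would then have no finite hazard ratio, no stated primary test and no fallback. The choice of test would be made after open-label data (section 9.1.4) had been seen. The power statement in 14.2 also belongs to a different test from the one in 14.7.1.

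**Working it through.** **Inputs.** From 14.2: control rate 11.5%, treated rate 3% (2% is also tabulated), 198 controls, 99 treated, 80% power, type I error 5%. From 14.7.1: censoring at 6 months. Assumed: exponential event times, complete follow-up and, unless stated, no weights. The 1% rate is not in the plan; it illustrates the range below 3%.

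**Step 1: reproduce the 80%.** Exact power of Fisher's test, 3% vs 11.5%, 99 vs 198, is 80.3% one-sided at 5% and 73.0% two-sided. The other nonparametric cells in the table also reproduce one-sided (80.1% to 80.3%). The stated figure is therefore a one-sided Fisher figure. Power for this kind of test does rise as the treated rate falls: two-sided it is 73%, 87% and 97% at 3%, 2% and 1%.

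**Step 2: expected events.** Treated: 99 × 0.03 = 2.97. Control: 198 × 0.115 = 22.8, taken as 23.

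**Step 3: probability of no treated events**, (1 − rate)^99:
- 3%: 0.97^99 = 0.049
- 2%: 0.98^99 = 0.135
- 1%: 0.99^99 = 0.370

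The number of controls does not enter.

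**Step 4: what happens at zero.** The partial likelihood keeps increasing as the coefficient goes to minus infinity, so no finite hazard ratio exists. The model-based standard error diverges and the Wald p-value goes towards 1. In simulation the robust standard error collapsed instead, and every zero-event trial looked significant, which is an artefact of non-convergence. Two software defaults can thus give opposite answers on the same data. Yet 0/99 vs 23/198 is strong evidence: Fisher two-sided p is about 0.0001.

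**Step 5: small non-zero counts.** With y treated events and 23 control events, approximate z = ln[(y/99)/(23/198)] / √(1/y + 1/23).

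| y | z |
|---|---|
| 1 | −2.39 |
| 2 | −2.37 |
| 3 | −2.19 |
| 4 | −1.95 |

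In simulation, two-sided Wald rejected in 97% of trials with one treated event, 90–93% with two, 76–77% with three and about 50% with four. Only zero breaks the test.

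**Step 6: a ceiling on Wald power.** If zero-event trials count as non-rejections, power cannot exceed 1 minus the Step 3 probability: 1 − 0.135 = 86.5% at 2% and 1 − 0.370 = 63% at 1%. The ceiling equals 80% when (1 − rate)^99 = 0.20, that is rate = 1 − 0.20^(1/99) = 1.6%. Below that, Wald cannot reach 80% whatever the sidedness or number of controls.

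**Step 7: simulated power**, unweighted Cox, 99 vs 198. Ranges span separate runs of 4,000 to 8,000 trials per scenario.

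| Treated rate | Wald, two-sided | Wald, one-sided | Score, two-sided | Likelihood ratio, two-sided |
|---|---|---|---|---|
| 3% | 65–66% | 79–80% | 74–75% | 79% |
| 2% | 71–72% | 79–80% | 88–89% | 91–92% |
| 1% | 58–60% | 61–62% | 97–98% | 98–99% |

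The usual events formula gives 91% at 3% and keeps rising. It assumes a normal log hazard ratio, so it cannot show the problem.

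**Step 8: weights.** The documents do not give the spread of the propensity weights. Assuming lognormal control weights, two-sided power at 3% / 2% / 1% was:
- log SD 0.5: robust Wald about 63% / 69% / 56% (zero-event trials not counted); robust score about 80% / 91% / 98%, with simulated size 5.2%
- log SD 1.0: robust Wald 52.2% / 58.4% / 49.6%; robust score 62.2% / 78.5% / 91.8%

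**The case against.** The strongest reply is that the plan never says Wald. Likelihood-ratio and score tests also test the coefficient, and their power rises below 3%. That stands: the loss belongs to one unstated choice, not to Cox regression. But testing a coefficient and exponentiating it reads most naturally as the coefficient-table test. The ordinary likelihood-ratio test is not strictly valid with weights, and the lack of a finite hazard ratio at zero does not depend on the test.

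A reader might infer four stronger things that the documents do not support:
- That few events break the analysis. Step 5 shows otherwise. Wald power does not fall between 3% and 2%, the two rates the plan tabulates.
- That the sentence in 14.2 is wrong. It describes the two-proportion calculation in its own section and is right for that. The gap is that the sizing test and the primary test differ.
- That the whole shortfall from 80% comes from Wald. Part is sidedness: the sizing test itself has only 73.0% two-sided, and the two-sided score test about 74–75% at 3%.
- That a zero-event trial would be reported as non-significant. Nothing says so; the plan is silent, and software could equally return a spuriously small p-value.

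It is also fair that the main simulation omits the weights, and the covariates named in the synopsis (route of administration and comorbid substance use disorder). Step 8 addresses the weights only under assumed spreads.

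**Conclusion.** The point holds as a gap in specification with a real consequence. At the planned 3% rate about 1 trial in 20 would have no treated events; at 2% about 1 in 7; at 1% more than 1 in 3. In each, the planned effect measure does not exist and the plan does not say what to report. These probabilities assume 99 treated subjects followed for the full 6 months and are otherwise exact.

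If the test is Wald, power levels off at about 71% two-sided or 79–80% one-sided near a 2% rate, then falls to about 58–60% or 61–62% at 1%. The power statement in 14.2 therefore does not carry over to the primary analysis under that reading. The figures rest on exponential times, 198 controls, no weights, and zero-event trials counted as non-rejections. Under the assumed weights the gap between Wald and score tests remains, but the absolute levels depend on a weight spread that the documents do not give.

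**What to change.** - **14.7.1, test.** Make the primary p-value a propensity-weighted score (log-rank) test with robust or resampling variance, and state its sidedness. Check its size under the weights actually obtained; the simulated size of 5.2% covers only one assumed spread.
- **14.7.1, zero events.** Pre-specify what is reported if no treated subject has an event: for example the weighted 6-month Kaplan-Meier risk difference with a resampling or exact interval, or a penalised hazard ratio whose interval is valid under the weights. An ordinary profile-likelihood interval should not be assumed valid there.
- **14.2.** Restate power for the named test and its sidedness. Say that the present 80% is a one-sided 5% Fisher figure (80.3%; 73.0% two-sided). For reference, the unweighted two-sided score test gives about 74–75% at 3%, 88–89% at 2% and 97% at 1%.

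The cost is SAP wording and a little more analysis work, with no change to data collection. The downside is that a two-sided test would show planned power below 80% at a 3% treated rate.
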